7.3 LOST TO FOLLOW-UP

A participant will be considered lost to follow-up if he or she fails to return for four scheduled visits and is unable to be contacted by the study site staff.

The following actions must be taken if a participant fails to return to the clinic for a required study visit:

- The site will attempt to contact the participant within one day of the missed visit and attempt to reschedule the visit. Study staff will counsel the participant on the importance of maintaining the assigned visit schedule and ascertain if the participant wishes to and/or should continue in the study.
- Before a participant is deemed lost to follow-up, the investigator or designee will make every effort to regain contact with the participant (where possible, 3 telephone calls and, if necessary, a certified letter to the participant's last known mailing address or local equivalent methods). These contact attempts will be documented in the participant's study file.
- Should the participant continue to be unreachable, he or she will be considered to have withdrawn from the study with a primary reason of lost to follow-up.

8 STUDY ASSESSMENTS AND PROCEDURES

8.1 EFFICACY ASSESSMENTS

Enrollment/Baseline/Testing Visit 1/Repeat Testing Visit 1

The following study procedures and evaluations will be performed at Testing Visit 1 (-30 days)) and may be repeated if the surgery is rescheduled making the visit fall outside of the 30 day window:

- Informed consent or assent (for participants under the age of 18 years of age)
- Urine pregnancy test for women of child bearing potential. Child bearing potential is defined as a premenopausal female capable of becoming pregnant.
- Concomitant medication review
- Height (cm) and weight (kg)
- Adverse event review and evaluation
- Anterior/Posterior (A/P)A knee X-ray. Briefly, participants will be positioned for the X-rays using a Synaflexer (BioClinica, Inc.) to ensure similar positioning across study time points. The X-ray tech at MedSport will be responsible for obtaining images.
- Clinical Knee X-ray - The knee x-rays that are gathered as part of standard clinical care for an ACL injury will be pulled from MiChart and used to determine patellar alignment. Specifically, from the lateral and patella "sunrise" views, we will use custom written MATLAB, semi-automatic software to determine measures of patellar alignment. From the sunrise view, edge detection will be used semi-automatically to identify the anterior margins of the femur and posterior margins of the patella. Anatomical landmarks required for the following measurements will be determined automatically and include the most anterior point of the medial and lateral femoral condyles, the deepest point of the intercondylar sulcus, apex of the patella, and the medial and lateral femoral and patellar facets. Measures reflecting trochlear

dysplasia will include sulcus angle and sulcus depth as described by Merchant et al.¹ Measures reflecting trochlear sulcus and patellar tilt will include the lateral patellofemoral angle and congruency angle. Patellofemoral index, ratio of medial and lateral patellofemoral joint space, will also be determined. From the lateral view, patellar height will be measured manually which reflects the ratio of the length of the patellar articular surface to the length of the patella tendon measured from the lower pole of the patella to the insertion into the tibia tubercle

- Study specific testing. Specialized measurements will be recorded by study staff (post-doctoral fellow, graduate students). Thigh muscle strength and quadriceps activation will require the use of a Cybex dynamometer equipped with both an anti-shear and a knee attachment. Biomechanics will be recorded with standard procedures using a Vicon Nexus motion capture system. Quadriceps/Knee Cartilage ultrasonography will be used to gather measurements of quadriceps atrophy and femoral cartilage thickness. An optional muscle biopsy may be gathered to assess markers of inflammation, muscle damage, and hypertrophy/atrophy. Biopsy may also be used for muscle phenotyping.
- Questionnaires
 - PROMIS Physical Function computer adaptive test (PF CAT): The National Institutes of Health (NIH) Patient-Reported Outcomes Measurement Information System (PROMIS®) Roadmap initiative (www.nihpromise.org) is a cooperative research program designed to develop, evaluate, and standardize item banks to measure patient-reported outcomes (PROs) across different medical conditions as well as the US population. The PF CAT is a broad instrument evaluating physical function in both upper and lower extremities; by responding to the test taker's selections in real time, it is able to reduce the number of questions needed to accurately ascertain a patient's functional status. A patient typically answers between 4-12 questions from a bank of 121 possible questions, and, usually, the test is completed in less than 1 minute. This test has demonstrated good-to-excellent construct validity in patients who have undergone ACL reconstruction.⁴¹
 - The Knee injury and Osteoarthritis Outcome Score (KOOS) is a knee-specific measure intended to examine patient reported outcomes after injuries that may lead to post-traumatic osteoarthritis, like an ACL injury. KOOS consists of 5 subscales: 1) Pain, 2) Other Symptoms, 3) Function in daily living (ADL), 4) Function in sport and recreation (Sport/Rec) and 5) knee related Quality of life (QOL). The previous week is the time period considered when answering the questions. Standardized answer options are given (5-point Likertscale) and each question is assigned a score from 0 to 4. A normalized score (100 indicating no symptoms and 0 indicating extreme symptoms) is calculated for each subscale.
 - The Tegner Activity Scale is a numerical scale with each value (0–10) representing specific activities. An individual who participates in competitive sports including soccer, football, and rugby at the elite level is considered to have an activity level of 10. An individual participating in the above listed sports but at the recreational level is considered to have an activity level of 6. An individual on sick leave or disability pension due to knee problems is considered to have an activity level of 0. The Tegner scale has proven valid, reliable, and responsive to change.⁴²

- The Marx scale is utilized to assess a person's level of physical activity. It focuses on four activities: running, deceleration, cutting, and pivoting. Participants are asked to indicate approximately how many times in the past 12 months they performed each of these activities while at their healthiest and most active state. The four knee functions are rated on a 5-point scale of frequency and scores are added up to a maximum of 16 points with a higher score indicating more frequent participation. This scale has been shown to be both valid and reliable.⁴³
- The Tampa Scale of Kinesiophobia (TSK-11) is a patient reported outcome developed to assess 'fear of movement-related pain' in patients with musculoskeletal pain. Each item is scored on a 4-point Likert scale, ranging from 1 'strongly disagree' to 4 'strongly agree'; total scores vary between 11 and 44, with higher scores indicating higher levels of fear of movement-related pain. Validity, Reliability, sensitivity, and specificity have all been established and fall in an acceptable to excellent range.⁴⁴

Intervention Visits 1-16 (For Randomized Participants Only)

The following study procedures and evaluations will be performed at Visit 1-16 (twice per week during Weeks 1-8):

- Randomization. At Intervention Visit 1, subjects will be randomized prior to the administration of the study intervention.
- Study Intervention. At Visits 1-16, NMES or placebo will be administered twice per week. Study intervention parameters will be recorded by the physical therapist.
- Concomitant medication review
- Adverse event review and evaluation
- Standard of Care Rehabilitation Assessment (to be collected until discharged from formal physical therapy)

Intervention Visits 17-32 (For Randomized Participants Only)

The following study procedures and evaluations will be performed at Visit 17-32 (twice per week during Weeks 9-16):

- Study Intervention. At Visits 17-32, ECC or placebo will be administered twice per week. Study intervention parameters will be recorded by the physical therapist.
- Concomitant medication review
- Adverse event review and evaluation
- Standard of Care Rehabilitation Assessment (to be collected until discharged from formal physical therapy)

Testing Visit 2

The following study procedures and evaluations will be performed at testing visit 2 (post-NMES intervention visit):

- Height (cm) and weight (kg)
- Adverse event review and evaluation
- Study-specific testing. Specialized measurements will be recorded by study staff (post-doctoral fellow, graduate students). Thigh muscle strength and quadriceps activation will require the use of a Cybex dynamometer equipped with both an anti-shear and a knee attachment. Quadriceps/Knee Cartilage ultrasonography will be used to gather measurements of quadriceps atrophy and femoral cartilage thickness.
- Questionnaires. The PROMIS questionnaire will be administered in order to assess participant perceived function. Knee injury and Osteoarthritis Outcome Score is a knee-specific measure intended to examine patient reported outcomes after injuries that may lead to post-traumatic osteoarthritis, like an ACL injury. Tegner and Marx scores will be assessed in order to examine participant's activity levels. The Tampa Scale of Kinesiophobia will be delivered to determine participant's fear of re-injury.
- For those in the standard of care group – patients will reach the testing visit 2-time point when they have completed 16 PT treatments – approximately 2x a week for 8 weeks.
- Special considerations will be made for those with insurance visit limitations such as patients will reach testing visit 2 when they have completed 8 PT treatments – approximately 1x a week for 8 weeks.
-

Testing Visit 3

The following study procedures and evaluations will be performed at testing visit 3 (post-ECC intervention visit):

- Height (cm) and weight (kg)
- Adverse event review and evaluation
- Study specific testing. Specialized measurements will be recorded by study staff (post-doctoral fellow, graduate students). Thigh muscle strength and quadriceps activation will require the use of a Cybex dynamometer equipped with both an anti-shear and a knee attachment. Quadriceps/Knee Cartilage ultrasonography will be used to gather measurements of quadriceps atrophy and femoral cartilage thickness. A muscle biopsy may be gathered to look at markers of inflammation, muscle damage, and hypertrophy/ atrophy. Biopsy may also be used for muscle phenotyping.
- Questionnaires. The PROMIS questionnaire will be administered in order to assess participant perceived function. Knee injury and Osteoarthritis Outcome Score is a knee-specific measure intended to examine patient reported outcomes after injuries that may lead to post-traumatic osteoarthritis, like an ACL injury. Tegner and Marx scores will be assessed in order to examine participant's activity levels. The Tampa Scale of Kinesiophobia will be delivered to determine participant's fear of re-injury.
- For those in the standard of care group – patients will reach the testing visit 3-time point when they have completed 32 total PT treatments – approximately 2x a week for 16 weeks.
- Special considerations will be made for those with insurance visit limitations such as patients will reach testing visit 3 when they have completed 16 total PT treatments – approximately 1x a week for 16 weeks.

Testing Visit 4

The following study procedures and evaluations will be performed at Testing Visit 4 (Week 36 [9 months post-ACLR]):

- Concomitant medication review
- Height (cm) and weight (kg)
- Adverse event review and evaluation
- Study specific testing. Specialized measurements will be recorded by study staff (post-doctoral fellow, graduate students). Thigh muscle strength and quadriceps activation will require the use of a Cybex dynamometer equipped with both an anti-shear and a knee attachment. Biomechanics will be recorded with standard procedures using a Vicon motion capture system. Clinical hop tests only require the use of a tape measure that will be attached to ground. Quadriceps/Knee Cartilage ultrasonography will be used to gather measurements of quadriceps atrophy and femoral cartilage thickness.
- Questionnaires. The PROMIS questionnaire will be administered in order to assess participant perceived function. Knee injury and Osteoarthritis Outcome Score is a knee-specific measure intended to examine patient reported outcomes after injuries that may lead to post-traumatic osteoarthritis, like an ACL injury. Tegner and Marx scores will be assessed in order to examine participant's activity levels. The Tampa Scale of Kinesiophobia will be delivered to determine participant's fear of re-injury.

Testing Visit 5

The following study procedures and evaluations will be performed at Testing Visit 5 (Week 72 [18 months post-ACLR]):

- Concomitant medication review
- Height (cm) and weight (kg)
- Adverse event review and evaluation
- A/P knee X-ray
- Magnetic Resonance Images. MRI images of the involved and uninvolved knees will be recorded to assess knee joint cartilage. Scans will be approximately 1 hour in length and will take place at University Hospital on the 3T Phillips Research Scanner. Positioning and sequences will be described in the MOP.
- Study specific testing. Specialized measurements will be recorded by study staff (post-doctoral fellow, graduate students). Thigh muscle strength and quadriceps activation will require the use of a Cybex dynamometer equipped with both an anti-shear and a knee attachment. Biomechanics will be recorded with standard procedures using a Vicon MX motion capture system. Clinical hop tests only require the use of a tape measure that will be attached to ground. Quadriceps/Knee Cartilage ultrasonography will be used to gather measurements of quadriceps atrophy and femoral cartilage thickness. An optional muscle biopsy may be gathered to look at markers of inflammation, muscle damage, and hypertrophy/ atrophy. Biopsy may also be used for muscle phenotyping.
- Questionnaires. The PROMIS questionnaire will be administered in order to assess participant perceived function. Knee injury and Osteoarthritis Outcome Score is a knee-specific measure intended to examine patient reported outcomes after injuries that may lead to post-traumatic osteoarthritis, like an ACL injury. Tegner and Marx scores will be assessed in order to examine participant's activity levels. The Tampa Scale of Kinesiophobia will be delivered to determine participant's fear of re-injury.

12 and 15 Month Physical Activity Assessments

In order to account for physical activity occurring between the 9 and 18 month testing visits, study staff will email participants a physical activity assessment questionnaire at 12 and 15 months post-ACLR. The assessment will include a modified Marx Questionnaire. The Marx Questionnaire will be modified to reflect a 3-month period rather than a 12-month period. This assessment will also inquire about specific sports/activities that study enrollees are participating in.

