2 INTRODUCTION

2.1 STUDY RATIONALE

Anterior cruciate ligament (ACL) injuries are both common and costly, with approximately 300,000 tears occurring annually, at a lifetime cost approaching \$8 billion dollars. While ACL reconstruction (ACLR) successfully restores knee laxity to within normal limits, current ACL rehabilitation is, in part, inadequate, as it fails to restore quadriceps strength. These clinically significant reductions in quadriceps strength limit the patients' ability to engage in physical activity, lead to a decreased quality of life, and are an independent predictor of the development of post-traumatic osteoarthritis (OA) that plagues over 50% of limbs within 10-20 years of ACLR.

Current ACL rehabilitation paradigms are inadequate, as they do not effectively target the mechanisms, muscle inhibition and altered muscle morphology, that lead to muscle weakness after ACL injury and ACLR. ACL injury results in a reflexive, neurological shutdown of the quadriceps muscle (i.e. muscle inhibition), while simultaneously changes in protein and genetic expression lead to altered muscle morphology (i.e. atrophy). Further, as muscle inhibition prevents full voluntary quadriceps activation, it can perpetuate changes in muscle morphology. Failure to treat both causes of quadriceps weakness is a critical problem with ACL rehabilitation as doing so prevents full muscle strength from being restored.

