9.4.1 GENERAL APPROACH

The design of this randomized controlled study is a placebo-controlled investigation of the combination of NMES and ECC vs NMES placebo + ECC placebo. Continuous variables will be summarized using descriptive statistics including n, mean, median, standard deviation, range (e.g., minimum and maximum). Qualitative variables will be summarized using counts and percentages. Summaries will be provided by treatment group and overall. Unless otherwise specified, statistical analyses will be performed using SAS Version 9 or higher. For the co-primary endpoints, the nominal significance level is 0.025 (two-sided test with a Bonferroni adjustment for two comparisons); for all other statistical tests, the nominal significance level is 0.05 (two-sided). p-values and confidence intervals will be reported.

Linear models will be used for most analyses (primary and key secondary endpoints that are

continuous), with terms for treatment group, type of graft, surgeon, age, gender and baseline in all models.

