9.4.3 ANALYSIS OF THE SECONDARY ENDPOINT(S)

All tests of secondary endpoints (e.g., T1 relaxation ratio at 18 months post-ACL, score on KOOS at 9 months post-ACLR) will be conducted at the two-sided 0.05 level, without adjustment for multiplicity, using comparable models as for the primary endpoints. The mITT analysis set will be used. Appropriate non-linear parametric or non-parametric tests may be applied if the assumptions of the model are not satisfied. Details will be presented in the SAP.

In addition, for endpoints used to assess secondary objective 1 (i.e., T1 relaxation ratio at 18 months post-ACL and T2 relaxation ratio at 18 months post-ACL), we will include articular cartilage injury and meniscus injury and treatment as covariates in the linear model.

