9.4.9 EXPLORATORY ANALYSES

Several planned exploratory analyses will be conducted:

- For the primary endpoints, we will incorporate articular cartilage injury and meniscus injury and treatment as covariates in the linear model, with attention to fit statistics to avoid over-fitting.
- For endpoints used to assess the secondary objective 1 (i.e. , T1 relaxation ratio at 18 months post-ACL and T2 relaxation ratio at 18 months post-ACL), we will also explore activity during the return to activity period, activity level prior to injury, BMI and other interaction effects to assess effect modification, with caution to avoid over-fitting
- We will also examine the ability of quadriceps strength at 9 months post-ACLR to predict changes in cartilage health at 18 months post-ACLR. To do this we will employ linear models with several parameterizations of strength (e. g. , continuous, quartiles, binary threshold), assessing the discrimination and calibration for the prognostic models (will include other potential factors in addition to 9-month post-ACLR strength). Additional relationships among variables, such as the correlation of T2 and T1rho MRI measures of OA to X-ray measure of OA, will be explored graphically, summarized descriptively, and modeled using multivariable linear or logistic models.
- We will examine change in quadriceps muscle strength and muscle volume from baseline to post-NMES intervention (testing visit 2) and post-ECC intervention (testing visit 3) in an attempt to understand the effects of the individual components of the combined NMES+ECC intervention.

Several exploratory analyses will be performed to assess the ability to reduce the NMES and

ECC intensity in the placebo treatment group so that it reflects a “true” placebo condition. The SOC control group is a group of participants who were eligible for the randomized controlled trial but refused and were willing to consent to an observational arm.

Specifically,

- The demographic and baseline variables will be summarized in the SOC control group (no NMES or ECC treatment) using equivalent tabular and graphical methods to those described in Section 9.4.5.
- The co-primary and key secondary endpoints will be summarized in the SOC control group for all observed cases.

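### The exploratory cartilage analysis in 9.4.9 treats post-randomisation activity as an effect modifier; an arm contrast or interaction conditioned on it need not estimate the treatment effect or true effect modification

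*Combined protocol and SAP*

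**What the plan says.** Section 9.4.9 opens with "Several planned exploratory analyses will be conducted". For the 18-month T1rho and T2 ratios it then says "we will also explore activity during the return to activity period, activity level prior to injury, BMI and other interaction effects to assess effect modification", and adds a caution about over-fitting. It does not separate the return-period variable from the pre-injury one, and it does not say when BMI is taken. It names no instrument for return-period activity. The emailed questionnaire in 8.1, collected "In order to account for physical activity occurring between the 9 and 18 month testing visits", is the natural source, although 8.1 attaches no model or endpoint to it.

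The planned cartilage comparison is elsewhere. Section 9.4.1 specifies linear models "with terms for treatment group, type of graft, surgeon, age, gender and baseline in all models". For the T1rho and T2 ratios 9.4.3 adds: "we will include articular cartilage injury and meniscus injury and treatment as covariates in the linear model". Neither section has an activity term.

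On timing, 8.1 places randomisation at Intervention Visit 1, which the schedule in 1.4 allows up to two weeks after surgery. The objectives table in section 3 puts return to activity at about 9 months. On mechanism, 2.1 says that quadriceps weakness limits the "ability to engage in physical activity, lead to a decreased quality of life".

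**The concern.** Pre-injury activity is fixed before allocation, so randomisation balances it on average and a treatment-by-pre-injury-activity interaction can be read as effect modification. Return-period activity is different. It is observed after all study treatment has ended. If the treatment restores strength, and strength governs how active people can be, it is partly an outcome.

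Two problems follow if an arm contrast is conditioned on it:

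- Any part of the treatment effect on cartilage that runs through activity is removed.
- Participants with equal activity in the two arms may have reached it for different reasons, such as pain or joint damage. The comparison at fixed activity is then no longer protected by randomisation.

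A treatment-by-later-activity interaction inherits both problems. The arms' cartilage-activity slopes can differ without any pre-existing trait changing the effect of treatment.

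At stake is the reading of an exploratory result placed beside the randomised cartilage comparison. An activity-conditioned estimate could differ from the randomised one and be reported as effect modification. Measuring activity better would not cure this, and the over-fitting caution in 9.4.9 addresses a different problem.

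**Working it through.** **The plan's own figure.** Section 9.2 gives 56 per arm, 20% drop-out (56 × 0.8 = 44.8, taken as 45), an effect of 0.7 SD in strength symmetry, two-sided alpha 0.025 and power of at least 80%. With 45 per arm the normal approximation gives 86.0% and the noncentral t gives 84.9%. The statement holds and does not bear on this point. The documents give no figure for the cartilage or activity analysis.

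**Formula.** By least squares, in SD units:

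activity-adjusted arm difference = unadjusted arm difference − a × s

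Here a is the arm difference in mean activity, and s is the pooled within-arm slope of the cartilage ratio on activity. The slope s combines any real effect of activity on cartilage with any association due to shared causes.

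**Inputs.**

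- 0.7 SD strength effect: section 9.2.
- 45 evaluable per arm: section 9.2, where it is stated for strength. Using it for MRI is an assumption.
- r, the strength-activity association: assumed, with a = 0.7 × r.
- s: assumed.

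**Standard error.** √(2/45) = 0.21 SD for the unadjusted contrast.

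**Bias, and rejection rate when there is no total effect** (two-sided 0.05; simulated, 6,000 runs per scenario):

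| r | a | s | −a × s | Adjusted test rejects |
|---|---|---|---|---|
| 0 | 0 | 0.3 | 0 | 4.8% |
| 0.3 | 0.21 | 0.1 | −0.021 | not simulated |
| 0.3 | 0.21 | 0.3 | −0.063 | 6.5% |
| 0.5 | 0.35 | 0.3 | −0.105 | 7.4% |
| 0.5 | 0.35 | 0.5 | −0.175 | 15.3% |

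The test without activity rejected in 4.8% to 5.5% of runs in the four simulated scenarios. If s is negative, the sign of the shift reverses.

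**Splitting s into its parts.** Suppose activity does not affect cartilage and the two share an unmeasured cause correlated 0.3, 0.4 or 0.5 with each. Then s = 0.09, 0.16 or 0.25. Pairing these with a = 0.21, 0.35 and 0.49 gives shifts of 0.21 × 0.09 = 0.02, 0.35 × 0.16 = 0.06 and 0.49 × 0.25 = 0.12 SD in size. Simulated rejection rates (4,000 runs each) were 4.8%, 5.6% and 8.8%.

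Now let activity also move the ratio:

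- By 0.2 SD per SD, with a = 0.35 and s = 0.2 + 0.09 = 0.29: the total effect is 0.35 × 0.2 = 0.07, and the adjusted value is 0.07 − 0.35 × 0.29 = −0.03.
- By 0.3 SD per SD, with a = 0.49 and s = 0.3 + 0.16 = 0.46: the total effect is 0.49 × 0.3 = 0.147, and the adjusted value is 0.147 − 0.49 × 0.46 = −0.08.

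The shifts are about 0.10 and 0.23 SD. The value a = 0.49 needs r = 0.7, which is high for an emailed self-report.

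**Limit of the check.** All of this concerns activity entered as a main effect. The treatment-by-activity interaction that 9.4.9 points to was not simulated, and its distortion is not quantified here.

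**The case against.** The strongest reply is that nothing the trial will rest on is touched. The tests for Secondary Objective 1 "will be conducted at the two-sided 0.05 level, without adjustment for multiplicity, using comparable models as for the primary endpoints", and those models omit activity. A reader might infer from 9.4.9 that the randomised cartilage contrast is biased. The documents do not support that: activity appears only in an exploratory bullet.

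A reader might also take the phrase in 8.1 about accounting for activity as a commitment to covariate adjustment. It states why a questionnaire is sent and names no model, so it does not show the defect and needs no change.

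Third, that treatment changes activity is inferred from 2.1. It is not documented. The hypotheses in section 3 make it plausible, since they expect better KOOS scores and longer hops in the active arm, but if the arms have equal activity the bias is zero. Fourth, 9.4.9 says only that activity will be explored, and 9.4 leaves the details to an SAP still to be written, so the final model form is unknown. Finally, how sport exposure relates to cartilage is a fair exploratory question.

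All of this stands, and it limits the reach of the point. It does not answer the remaining defect: 9.4.9 offers a post-randomisation variable as an effect modifier on the same footing as a baseline one, with no guidance on how the result may be read.

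**Conclusion.** The point holds for the exploratory T1rho and T2 analyses in 9.4.9 and no further. Return-period activity is post-randomisation by its timing and plausibly affected by treatment on the protocol's own reasoning. A contrast or interaction conditioned on it therefore need not estimate the treatment effect or true effect modification.

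Its size cannot be found from the documents. For main-effect adjustment the bias is −a × s: zero with no arm difference in activity, and about 0.02 to 0.2 SD across the assumed inputs with a of 0.21 or more. Most of that range is well below the standard error, and only its upper end is comparable to it. The 15.3% rejection rate belongs to one corner of the assumed grid. The sign changes shown move between values that each lie within one standard error of zero. They show that the direction is not dependable, and do not predict a reversal. This is a modest weakness in interpretation, worth correcting because the correction is nearly free.

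**What to change.** In 9.4.9 and the SAP:

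1. Limit effect modifiers and added covariates in the T1rho and T2 treatment comparisons to variables fixed before randomisation: pre-injury activity, baseline BMI and the injury factors. Naming baseline BMI matters because weight is measured again at later visits.
2. Report 12- and 15-month activity by arm as an outcome.
3. Label any further analysis that conditions on return-period activity as descriptive or as mediation, state its assumptions, and add a sensitivity analysis for unmeasured common causes of activity and cartilage.

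Sections 8.1, 9.4.1 and 9.4.3 need no change on this account. The cost is wording and a little extra analysis work. No new data are needed and no confirmatory test changes. Section 9.4 has the SAP finalised before database lock and unblinding, so the change can be made there.
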